7.3.2. Reporting of serious adverse events

The investigator shall report all SAEs immediately within 24 hours after he becomes aware of the event by fax or e-mail to the Sponsor-PV. General information on the patient (pseudonymized), the randomization number, diagnosis and measures already taken are to be reported. The immediate report shall be followed by detailed written reports, sent within 5 business days. The investigator is obliged to completely document the course of the event and the measures taken, if possible, including the original findings and using the form for SAEs. Additional documentation is carried out on the case report forms.

SAE reports should be emailed/faxed to Sponsor-PV:

QPPV: [REDACTED] (business hours)
Email: [REDACTED]
Mobile: [REDACTED]
FaxToMail: [REDACTED]

The Sponsor will notify the Investigators of any Suspected Unexpected Serious Adverse Reactions (SUSAR) in accordance with local regulatory requirements and ICH GCP. In accordance with European Union (EU) Regulation 536/2014 of 16 April 2014 on clinical trials on medicinal products for human use (CTR), the Sponsor will collect and report any SUSARs to the Competent Authority/ies (via Eudravigilance for EU Countries). In addition, the Sponsor will inform the relevant Institutional Review Boards (IRBs) or Independent Ethics Committees (IECs) of SUSARs in accordance with local regulatory requirements and ICH GCP, unless locally this is an obligation of the Investigator.

The Sponsor shall ensure that all relevant information about suspected unexpected serious adverse reactions (SUSAR) that are fatal or life-threatening is recorded and reported as soon as possible to the competent authorities in the modalities required by the local regulations, and in any case no later than seven days after knowledge by the Sponsor of such a case, and that relevant follow-up information is subsequently communicated within an additional eight days.

All other SUSARs shall be reported to the competent authorities concerned and to the ethics committee concerned as soon as possible but within a maximum of fifteen days of first knowledge by the Sponsor accordingly.

The PV-Sponsor shall also inform all investigators.

7.4. Urgent safety measures and other relevant safety reporting

Where an unexpected event is likely to seriously affect the benefit-risk balance, the sponsor and the investigator will take appropriate urgent safety measures to protect the patients. In addition the sponsor will notify the CAs according to modalities required by local regulations. That notification will be made without undue delay but no later than 7 days from the date the measures have been taken.

7.5. Emergency procedures

Randomization will be supported by an interactive web response system (IWRS) to ensure study medication assignment according to stratification.

The sites will have access to the interactive web response system (IWRS) and will receive instructions how to use the system. Neither the patient nor the investigational staff will know which IMP a patient will be receiving. Where safety reasons may be warranted, and for those study members with appropriate access rights (including all study investigators) unblinding of a patients' treatment allocation will be possible via the IWRS.

7.6. Unblinding

- Unblinding by the request of the investigator should occur only in the event of an AE or SAE for which it is necessary to know the treatment to determine an appropriate course of therapy for the patient. The investigator may only request that the code is opened in the case of an emergency and when the identity of the study medication is crucial for emergency treatment
- The trial blind should not be broken except in case of a medical emergency (where knowledge of the IMP received would affect the treatment of the emergency) or regulatory requirement (e.g., for SUSAR)
- The unblinding of a patient treatment allocation is possible via the IWRS module, it must be performed only when serious safety reasons may be warranted, and only Investigators (Principal Investigator and his/her delegate) can perform this procedure
- If the blind is broken, the date, time, person who broke the blind and the reason must be recorded in the patient's eCRF, and any associated AE report
- If unblinding occurs, the patient must be discontinued from the trial.

7.7. Pregnancies

Pregnancies occurring during a patient's participation in a clinical trial, although not typically considered a SAE, must be notified to the Sponsor-PV within the same timelines as a SAE (within 24 hours after being made aware of the pregnancy) on a pregnancy notification form. The pregnant trial patient should be withdrawn immediately from the trial.

Pregnancy should be emailed/faxed to Sponsor-PV:

QPPV: [REDACTED] (business hours)

Email: [REDACTED]

Mobile: [REDACTED]

FaxToMail: [REDACTED]

Any pregnancy that occurs in a trial patient should be followed up until outcome. If relevant, the development of the newborn has to be monitored for an appropriate time post-delivery, but only if written consent of parents (or only one parent depending on local regulations) is provided.

8. Discontinuation criteria

8.1. Premature termination of the trial

The sponsor is under obligation to monitor the progress of the clinical trial with regard to safety-relevant developments and, if necessary, initiate the premature termination of the clinical trial. The sponsor will be supported in this responsibility by the DSMB, with particular attention for children. The clinical trial must be terminated prematurely if:

- the benefit-to-risk ratio for the patients changes markedly
- the sponsor or the DSMB considers that the termination of the trial is necessary
- indications arise that the trial patients' safety is no longer guaranteed
- an insufficient recruitment rate makes a successful conclusion of the clinical trial unrealizable/no longer feasible
- the responsible Competent Authority (CA) revokes its approval.

The Sponsor reserves the right to discontinue the trial at any time for clinical or administrative reasons.

If the trial is prematurely terminated or suspended for any reason, the investigator has to notify the patients and to assure appropriate follow-up.

The Sponsor will promptly inform the investigators/institutions, and the regulatory authorities and EC of the termination or suspension and the reason(s) for the termination or suspension by the modalities and timelines according to applicable regulations.

8.2. Premature termination of the trial at one of the trial sites

Both the investigator and the sponsor have the right to terminate the trial at one of the sites.

The clinical trial can be terminated prematurely at his site by the investigator if, for instance unforeseeable circumstances have arisen at the trial site which preclude the continuation of the clinical trial, the investigator considers that the resources for continuation are no longer available, the investigator considers that the continuation of the trial is no longer ethically or medically justifiable.

The sponsor can initiate the exclusion of a site from further participation if, for instance, patient recruitment is inadequate, serious problems arise with regard to the quality of the collected data which cannot be resolved.

Premature termination at one of the trial sites does not automatically mean a termination of the trial for already enrolled trial patients. A separate decision on further treatment must be made for each patient, depending on the overall situation. Adequate further treatment and follow-up of already enrolled trial patients must be ensured. The documentation of already enrolled trial patients will be reviewed for completeness and plausibility. Queries may be raised for further clarification before the site is closed. These queries must be answered properly by the site. The CA(s) and IEC(s) must be duly notified of the site's closure, including reasons, within the specified period, according to applicable regulations. The trial site concerned will be closed in stages by the CRA when a decision has been made on the further treatment of the patients concerned.

8.3. Discontinuation of trial treatment or trial participation for individual patients

8.3.1 Premature discontinuation of trial treatment

The trial patient can have his/her trial treatment terminated prematurely at any time, without having to give reasons.

Patients will be withdrawn from the treatment if their safety or well-being is at risk. Discontinuation will be made at the discretion of the investigator/Sponsor/DSMB or at the patient's request.

The investigator should contact the Sponsor to discuss the withdrawal of a patient who fulfils the discontinuation criteria, prior to discontinuing a patient from the study, unless in those circumstances where the investigator considers that the patient is at immediate clinical risk.

A patient must be discontinued under the following circumstances:

- Withdrawal of consent
- IMP permanent discontinuation for any reason in one or both treated areas
- Pregnancy
- An AE, including intercurrent illness for which the patient desires to discontinue treatment or the investigator determines that it is in the best interest of the patient to be discontinued
- In case of unexpected laboratory out-of-range values in the blood samples collected at screening, which in the Investigator's opinion may pose the patient at increased risk during participation to the clinical trial the patient will be contacted to discontinue the treatment and will be withdrawn from the study.
- Serious concomitant symptoms (e.g., extensive blisters or erosions) in the facial area as well as a local or generalized allergic reaction to the IMP or procedures
- Lost to follow-up.

A patient may be required to discontinue from the trial at any time for the following reasons:

- The patient's treated and not treated acne worsens and requires alternative or supplemental medication during the trial.
- Occurrence of another dermatosis requiring treatment that interferes with the inclusion criteria
- Subsequent disclosure that the inclusion and exclusion criteria were not fulfilled when the patient was enrolled in the trial if the safety and well-being of the patient might be influenced
- At the discretion of the investigator
- Non-compliant use of IMP or protocol requirements
- Treatment code is broken.

In the case trial treatment of a patient has been stopped prematurely, ETV procedures should be conducted as far as possible. The DSMB will be informed accordingly, and all the relevant information provided.

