Concomitant medications should be kept to a minimum during the clinical trial. However, if they are considered necessary for the patient's welfare and are unlikely to interfere with the study objectives, they may be allowed at the discretion of the investigator. For a detailed list of forbidden medication see exclusion criteria. In case of doubts the Sponsor should be asked.

Rescue medication:

No formal rescue medication is foreseen. Patient requiring substitutive treatment for acne, as per Investigator's judgement will be discontinued from the study and relevant details documented.

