- Collection of IMP and diary and assessment of patient compliance by diary check, and counting of tubes
- Schedule next visit.

Follow-up

Visit 6 (Wk14) End of trial Day99 (+ 2days) or ETV in case of withdrawal after EoT – Telephone contact

- Check concomitant medications/therapies and AEs
- End of trial.

If clinically significant out of range or clinically significant values are found at V5, patient will be asked to return at site to perform additional laboratory examinations of the significant out of range values.

This visit will be performed only for patients who are not included in the long-term study.

UNSCHEDULED VISITS (Early termination visit [ETV])

Any time the trial is permanently discontinued for any reason during the treatment phase, an Early Termination visit should be performed:

- Check concomitant medications/therapies and AEs
- Physical examination and measurements of vital signs (blood pressure and heart rate [pulse])
- Collection of samples for determination of laboratory parameters:
 - Standard safety laboratory examinations
 - Blood pregnancy test in childbearing potential women (see **Appendix C** for definition of WOCBP)
- Clinical assessments (lesion count [inflammatory and non-inflammatory lesions] and IGA/PGA). PGA will be evaluated only if the trunk is treated
- [REDACTED]
- [REDACTED] (not mandatory, following specific consent)

- Dermatology Life Quality Index (DLQI) / Children's Dermatology Life Quality Index (C-DLQI for patients from 9 to 16 years old), completed by the patient (prior to any Investigator assessments to not impact the patient's answers to the quality of life questionnaire)
- Evaluation of local tolerability signs/symptoms. The patient will be questioned if he/she experienced any of these subjective symptoms within the last 24 hours prior to visit
- Patient's assessment of overall application site irritation
- Collection of IMP and diary and assessment of patient compliance by diary check, and counting of tubes
- End of trial.

In case the discontinuation is during the Follow-up phase, the Visit 6 (Wk14) End of trial (± 2 days) – Telephone contact procedures will be performed.

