6.6.1. Efficacy analyses

6.6.1.1. Primary analysis

The primary variables will be analyzed presenting descriptive statistics (mean, SD, median, IQR, minimum and maximum for total [REDACTED] endpoint and count and percentage for IGA success rate endpoint) overall, by treatment arm and, if deemed relevant, by study visit.

Subgroup analyses will be performed for: gender (M; F), age (≥ 9 and ≤ 18 years; vs ≥ 19 and < 50 years; and also in the following subgroups ≤ 12 ; 13 to 18; ≥ 19), IGA/PGA, Race/ethnicity (White; Black; Asian, Latino; other); Fitzpatrick skin type; country.

Absolute and relative differences in terms of total [REDACTED] between baseline and EoT will be also presented.

Estimands for the primary Endpoint 1 (E1)

The estimand for the primary E1 is defined as follows:

1. Treatment: 12 weeks administration of NAC-GED-0507 gel [REDACTED]% or vehicle gel.
2. Target population: Male and female patients aged ≥ 9 and < 50 years affected by facial acne vulgaris. Full Analysis Set.
3. Variable: relative change from baseline in total [REDACTED] (inflammatory plus non-inflammatory) at V5/Wk12 on the face.
4. Intercurrent events (ICEs) and strategies to handle them:
 - Treatment discontinuation

- Study withdrawal
- Use of prohibited medications listed in section 5.4.7

A treatment policy strategy will be applied where all observed values will be used regardless of the occurrence of the ICEs. Missing data due to any reason will be handled by using a LOCF imputation

5. Population-level summary: the difference in the relative change from baseline to V5/Wk12 in total [REDACTED] between the two treatment groups will be assessed by an independent t-test (or a Wilcoxon test if the Normality is violated). A p-value equal to or lower than 0.05 will be considered statistically significant.

Estimands for the primary Endpoint 2 (E2)

The estimand for the primary E2 is defined as follows:

1. Treatment: 12 weeks administration of NAC-GED-0507 gel [REDACTED]% or vehicle gel.
2. Target population: Male and female patients aged ≥ 9 and <50 years affected by facial acne vulgaris. Full Analysis Set.
3. Variable: proportion of patients with an IGA success at V5/Wk12.
4. Intercurrent events (ICEs) and strategies to handle them:
 - Treatment discontinuation
 - Study withdrawal
 - Use of prohibited medications listed in section 5.4.7.

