6.6.1.3. Sensitivity analysis

The same analysis performed on the primary endpoints will be conducted on the PPS as sensitivity analysis.

Additionally, a second sensitivity analysis performed on the FAS will be conducted using the following specifications:

Sensitivity Estimands for the primary Endpoint 1 (E1)

1. Treatment: 12 weeks administration of NAC-GED-0507 gel ■% or vehicle gel.
2. Target population: Male and female patients aged ≥ 9 and <50 years affected by facial acne vulgaris. Full Analysis Set.
3. Variable: relative change from baseline in total ■■■■■ (inflammatory plus non-inflammatory) at V5/Wk12 on the face.
4. Intercurrent events (ICEs) and strategies to handle them:
 - Treatment discontinuation
 - Study withdrawal
 - Use of prohibited medications listed in section 5.4.7

A treatment policy strategy will be applied where all observed values will be used regardless of the occurrence of the ICEs. Missing data due to any reason will be handled by using a multiple imputation approach with a missing-at-random (MAR) assumption

5. Population-level summary: the difference in the relative change from baseline to V5/Wk12 in total ■■■■■ between the two treatment groups will be assessed by an independent t-test (or a Wilcoxon test if the Normality is violated).

Sensitivity Estimands for the primary Endpoint 2 (E2)

1. Treatment: 12 weeks administration of NAC-GED-0507 gel ■% or vehicle gel.
2. Target population: Male and female patients aged ≥ 9 and <50 years affected by facial acne vulgaris. Full Analysis Set.
3. Variable: proportion of patients with an IGA success at V5/Wk12.
4. Intercurrent events (ICEs) and strategies to handle them:
 - Treatment discontinuation
 - Study withdrawal
 - Use of prohibited medications listed in section 5.4.7

A treatment policy strategy will be applied where all observed values will be used regardless of the occurrence of the ICEs. Missing data due to any reason will be handled by using a multiple imputation approach with a missing-at-random (MAR) assumption

5. Population-level summary: the difference in terms of the proportion of patients with an IGA success at V5/Wk12 between the two treatment arms will be assessed with an independent Chi-Square test (or Fisher exact test if the successes in one of the two treatment groups is lower than 5).

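### Both primary estimands claim treatment policy for stopping the gel, but a permanent gel stop ends trial participation, so the facial Week-12 outcome after it is not collected by design

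*Protocol*

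**What the plan says.** **Estimands.** For both co-primary endpoints, Section 6.6.1.1 names three intercurrent events: "Treatment discontinuation", study withdrawal, and use of prohibited medication. The handling is the same for all three: "A treatment policy strategy will be applied where all observed values will be used regardless of the occurrence of the ICEs". For gaps: "Missing data due to any reason will be handled by using a LOCF imputation". The sensitivity estimands in Section 6.6.1.3 keep the treatment-policy wording and change only the imputation: "Missing data due to any reason will be handled by using a multiple imputation approach with a missing-at-random (MAR) assumption".

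**Conduct.** Section 8.3.1 lists circumstances in which a patient must be discontinued. One is "IMP permanent discontinuation for any reason in one or both treated areas". After a premature stop of treatment the same section calls for the early termination visit (ETV) procedures. Section 5.5.1 introduces that visit so: "Any time the trial is permanently discontinued for any reason during the treatment phase, an Early Termination visit should be performed". Its procedures include the lesion count and IGA, and the last item on the list declares the trial over for that patient. The visit schedule in Appendix A labels this column as withdrawal and has no visit for a patient who is off the gel but still in the trial.

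**Endpoints.** Under Section 6.3.1 and the synopsis, both co-primary endpoints are facial and are measured at V5/Week 12.

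**The concern.** A treatment-policy effect needs the outcome at the planned time whether or not the patient is still on treatment. The estimands treat stopping the gel and leaving the study as two events, but the conduct rules merge them. Once the gel is stopped, the value that the strategy would use is not scheduled to be measured.

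This is a data-collection rule, so a statistical analysis plan cannot repair it afterwards. The reasons for stopping named in the protocol include adverse events, local reactions and a need for other acne treatment. These can be related to outcome and can differ by arm. The trial could then report as treatment policy an effect that, for stoppers, rests on imputed values. Part of the loss is also avoidable: a patient who stops only on the trunk leaves without a Week-12 assessment of the face.

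**Working it through.** **1. Does discontinuation in Section 8.3.1 mean the gel or the trial?** The trigger is already a permanent stop of the gel. Reading the consequence as stopping the gel would be circular. The same section speaks of discontinuing a patient from the study, and the ETV list in Section 5.5.1 ends the trial. The consequence is the end of participation.

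**2. What facial data exist after a gel stop?** The ETV count and IGA, taken at about the time of stopping. This is a Week-12 value only if the stop happens to fall close to Day 85.

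**3. What fills Week 12?** In the primary analysis, LOCF carries forward an earlier value, from the last visit or the ETV (Sections 6.6.1.1 and 6.7). In the sensitivity analysis, multiple imputation under missing at random has no planned off-treatment Week-12 data to learn from, so it borrows from patients who continued. The per-protocol set requires study completion (Section 6.2). None of these estimates the treatment-policy effect for stoppers.

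**4. The other events, side by side.**

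| Event | Listed in the estimands? | Mandatory wording | Optional wording |
|---|---|---|---|
| Permanent gel stop | Yes | 8.3.1 | none |
| Need for substitutive acne treatment | Not by that name; prohibited medication is listed | Synopsis and 5.4.7: "will be discontinued from the study and relevant details documented" | 8.3.1 (may) |
| Unblinding | No | 5.4.5, 7.6, Appendix D: "If unblinding occurs, the patient must be discontinued from the trial" | 8.3.1 (may) |

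A patient who uses a prohibited product but stays on the gel need not leave under Section 8.3.1 and can have a V5 value.

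**5. The plan's own figures.** Section 6.5 gives 366 evaluable and 400 enrolled patients. (400 − 366)/400 = 34/400 = 8.5%, and 366/(1 − 0.085) = 400, so the two figures fit together. The 366 itself cannot be reproduced, because the effect sizes, SD, vehicle rates and dropout rate are redacted.

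**6. Size under assumptions.** Let *s* be the share of each arm that stops early, and *b* the amount by which LOCF overstates Week-12 IGA success among active-arm stoppers, with no error under vehicle. Neither figure is in the protocol. The shift in the arm difference is *s* × *b*:

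| *s* | *b* = 10 points | *b* = 20 points | *b* = 30 points |
|---|---|---|---|
| 5% | 0.5 | 1.0 | 1.5 |
| 10% | 1.0 | 2.0 | 3.0 |
| 15% | 1.5 | 3.0 | 4.5 |

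**7. Worst case.** With a share *m* missing in each arm and observed difference *D*, the full-sample difference lies between (1 − *m*)*D* − *m* and (1 − *m*)*D* + *m*. The bound is therefore ± *m*, for example ± 10 points at an assumed 10%. It is reached only if every missing patient in one arm is a success and every one in the other a failure.

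**The case against.** **Section 8.3.1 is headed as discontinuation of treatment, and 8.3.2 deals with participation separately.** True, and the headings may show the intention. The text under 8.3.1 and the ETV list do not carry it out, for the reasons in step 1.

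**Treatment policy works for some events.** This stands. A reader might infer that no Week-12 value is collected after any listed intercurrent event. The documents support that for a gel stop only. Values after withdrawal of consent cannot be obtained under any rule.

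**Facial data are not lost altogether.** This stands too. A trunk-only stopper should have a facial count and IGA at the ETV, and LOCF may carry that value rather than an older one. What is missing is the Week-12 value.

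**Unblinding does not show a mismatch with the estimand.** Correct, since it is not a listed intercurrent event. It matters here only because the passages on it conflict.

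**The effect may be small.** The protocol gives no discontinuation rates. Its Phase 2b figures for patients with adverse events, 19% and 16% on the two active gels and 19% on vehicle (Section 3.2), do not suggest a strong imbalance. The Phase 2b age subgroups in the synopsis showed IGA differences of 20.5 and 22 points, for which 183 per arm gives about 99% power on IGA alone. This limits the likely effect on the trial's conclusion. It does not make the estimand label correct.

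**Conclusion.** The contradiction is real and lies in the current text. For permanent gel discontinuation, the treatment-policy strategy claimed in both primary estimands, and repeated in both sensitivity estimands, cannot be carried out with the data that the protocol collects. The conflicts between mandatory and optional wording on substitutive acne treatment and on unblinding also have to be reconciled.

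The size is unknown. Under the one-sided LOCF assumption the IGA difference shifts by 0.5 to 1.5 points at 5% stopping and by 1.5 to 4.5 points at 15%. The documents do not fix the direction of the error.

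Two stronger readings are tempting and not supported. First, the 8.5% implied by 366 of 400 is not an expected rate of missing Week-12 values. It allows for patients outside the full analysis set, and an early stopper with one valid post-baseline assessment of both endpoints stays in that set and is imputed. Second, the worst-case bound is a limit on an assumed rate, not an expected bias.

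**What to change.** Leave the clinical stopping rules as they are.

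1. In Sections 8.3.1 and 5.4.7 and in the ETV text of 5.5.1, separate stopping the gel from leaving the trial. Reconcile the passages on substitutive acne treatment (synopsis, 5.4.7, 8.3.1) and on unblinding (5.4.5, 7.6, Appendix D, 8.3.1).
2. Ask patients who stop the gel and still consent to attend the already defined V5 (Day 85) for the facial lesion count and IGA. Record off-treatment status and any other acne treatment.
3. Flag any V5 rating from an unblinded patient and examine it in a sensitivity analysis, because the investigator who broke the blind may also be the rater.
4. If steps 1 and 2 are not adopted, restate the strategy in both primary and both sensitivity estimands to match the data collected, and drop the treatment-policy claim for treatment discontinuation.

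Cost: a protocol and consent amendment and a few off-treatment visits, which some patients will decline. Step 4 alone needs only a change of wording, but it gives up the treatment-policy estimate for patients who stop.
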